- a. Lengthen the time window of treatment for patients with fCIS from 6 hours to 24 hours. In doing so, we will offer useful treatment to patients who would otherwise be denied treatment under current standards.
- b. Encourage focusing on achieving good revascularization rather than limiting time during IAT for patients with fCIS.
- c. Improve the percentage of good outcomes in the treated population
- d. Save patients with pCIS from complications due to brain edema and intra-cranial hemorrhage that could potentially result from IAT
- e. Save the health care system the costs of futile treatment of patients with pCIS.

III. METHODS

A. Study Design:

Version: 6.0

The current study focuses on patients with acute ischemic stroke due to a blockage of the intracranial internal carotid artery or middle cerebral artery (M1). The study will be performed prospectively in up to 6 stroke centers. Akron General Medical Center is the primary institution for development of the study and data analysis for this multicenter trial. To participate in the study, all centers need to meet certain qualified requirements which include:

- One neurointerventionalist with 6 years' experience in performing IAT with multiple devices.
- Demonstrate coverage of the comprehensive stroke center 24 hours a day. The proposed study will be carried out over a period of 4 years from the initial approval date. Informed consent will be obtained for each patient, as described in section VIII. The study will be carried out in 2 phases (Figure 1).

Phase I will compare outcomes between treated patients with fCIS and pCIS. All eligible patients will be assessed by a full diagnostic cerebral angiogram with dye injection of all potential collaterals. DCA will be used to characterize the CIS. Treatment will be identical for both groups. All patients will be treated with the combination of IAT and the normal standard of care for a patient not receiving IAT (which may include IVT, but not always). The sample size will be set to have 60 patients complete the trial. Distribution of fCIS and pCIS patients will not be forced, but the option to balance groups may be employed if the percentage for one group reaches 70%.

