Pre-operative condition and patients outcomes will be assessed using standardized and validated measures. The primary endpoint of a mRS score will be obtained at least 90 days following treatment and again at 1 year following treatment. NIHSS score will be obtained in the emergency room before the treatment, within 24 h of treatment, and before discharge. The person who will obtain the NIHSS will be certified to obtain it. Adequacy of revascularization will be assessed at the end of treatment by the treating physician according the modified thrombolysis in cerebral infarction (mTICI) scale (see Appendix). All of these measures are standards for care and trials of acute ischemic stroke. [8-10] All case report forms will be maintained by the primary investigator at the local site, and stored within locked cabinets. The personal identifying information on the case report forms will be deidentified and assigned a code before being transferred to Akron General Medical Center for transfer of the data to a de-identified database which will be used for analysis.

IV. DATA COLLECTION

Version: 6.0

A. How and what data will be collected

Data related to patient demographics, stroke risk factors, condition prior to treatment, time of treatment, and outcomes will be collected for each patient. Data on demographics will include sex, age, and race. Data on stroke risk factors will include history of hypertension, blood pressure, prior heart attack, arrhythmias, diabetes, glucose (sugar) level at admission, and obesity. Data on condition prior to treatment will include NIHSS score determined in the emergency room. Data on time of treatment will include time from symptoms to arrival at emergency room, time to start of DCA, and time to end of the procedure. Data on outcomes will include mRS at 3 months, mRS at 1 year, NIHSS score within 24 hours and at discharge, and complications brain edema and intra-cranial hemorrhage. Other parameters within these categories could be acquired as deemed necessary for analysis of the data.

V. DATA ANALYSIS

A. Sample Size Considerations

Phase I

A power analysis has been performed based on the previous retrospective analyses of the relationship between outcomes and the CIS for phase I. The sample size was calculated for the influence of the combination of CIS and revascularization on good outcomes (mRS \leq 2) based on the following assumptions.

- The percentage of patients with fCIS will be 60%

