- The percentage of patients with good revascularization will be 50%
- The rate of good outcomes for the combination of fCIS and good revascularization is assumed to be 70%
- The rate of good outcomes for the combination of fCIS and poor revascularization is assumed to be 20%
- The rate of good outcomes for the combination of pCIS and good revascularization is assumed to be 20%
- The rate of good outcomes for the combination of pCIS and poor revascularization is assumed to be 10%

The assumptions provide the following power analysis:

- $\alpha = 0.05$ for overall analysis and set to 0.025 for subgroup analysis comparing fCIS and good revascularization to all other groups due to multiple comparisons
- power = 0.90
- Needed Sample size = 54 patients
- An additional 6 patients completing the trial are budgeted due to risk of errors in estimated outcomes. An additional 15-20 patients are expected to be enrolled due to patients lost to the 90 day follow up and/or deviations from the protocol.

Phase II

Phase II will be an exploratory study evaluating the rates for good outcomes for patients with pCIS treated with IVT plus IAT vs. IVT (or other standard of care) only. The rate of good outcomes is expected to be approximately 13% for the IAT group with revascularization. The investigators have no prior data on expected rates of good outcomes for patients with pCIS treated with IVT only. The best possible outcome rate would be on

Version: 6.0

the order of 25% noted previously for untreated acute ischemic stroke. Due to the low levels of good outcomes, the investigators acknowledge the study will be underpowered to detect a difference between the two treatment groups for a total sample size of 30. Phase II will serve as a pilot study to initially establish estimates of rates of good outcomes for pCIS patients treated with IVT only for design of a larger prospective study.

Genetic Analysis

Genetic analysis will be performed based on the following:

- Genetic and expression analysis for the two groups based on their collateral score
- Adjust groups for cardiovascular/stroke risk factor presence and other known confounding conditions
- High density SNP array analysis will be performed for common and rare alleles
 against known collateral-related genes that have been identified in mice. These
 include human RABEP2 and its isoform RABEP1 and related gene pathways;
 VEGFA, FLK1 and their related gene pathways; NOTCH, DLL4, ADAM10,

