 ADAM17, CNX37 and their related gene pathways.
- Subgroup analysis will be performed for ethnicities.
- Taqman assays and/or exome sequencing of significantly associated SNPs and/or genes.
- Pending results, a future validation study will follow this discovery study by increasing the sample size.

B. Statistical Methodology

Data for the proposed study will be analyzed using comparison of proportions and multivariable logistic regression. Analysis of proportions based on Fisher exact tests will be used to compare rates of good outcomes between the fCIS and pCIS groups as the primary end point for phase I. The influence of successful revascularization on outcomes for patients with fCIS or pCIS will also be analyzed using Fisher exact tests as the secondary end point.

Binary and/or ordinal multiple logistic regression analyses will be used to evaluate the influence of multiple parameters on the likelihood of a good outcome. These parameters will include CIS, mTICI score, NIHSS score, time to revascularization, age, sex, history of diabetes mellitus, history of high blood pressure, history of coronary artery disease. The same analyses will be performed for phase II, instead focusing on the treatment groups rather than the CIS classification.

VI. DATA AND SAFETY MONITORING PLAN

A. Describe any provisions for monitoring the data for safety

A safety committee will monitor the data. The safety committee will be composed of at least 3 voting members. At least two members will be neurologists, neuroradiologists or neurointerventionalists with experience treating acute ischemic stroke who are not investigators at any of the sites. These members will not be affiliated with the institution of the principal investigator, any sub- investigator, or Akron General Medical Center. At least one member with a background in biostatistics who is not an investigator or affiliated with Akron General Medical Center will also be on the committee.

For phase I, the only deviations in normal standards of care are:

Version: 6.0

- 1- the extra few minutes for full DCA for some centers as opposed to injecting only the occluded vessel
- 2- Adding IAT to treatment of patients seen between 6 and 24 hours of onset of symptoms.

The safety committee will be looking at known potential complications for IAT in both fCIS and pCIS groups. These include:

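### The supportive nine-parameter logistic regression has about 20 good outcomes in Phase I and 4 to 6 in Phase II. Fitted as a binary model by ordinary maximum likelihood, it biases the CIS odds ratio upward and in Phase II often has no finite solution.

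*Combined protocol and SAP*

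**What the plan says.** Section V.B makes Fisher exact tests the primary and secondary analyses of Phase I. It then adds multiple logistic regression, which may be binary, ordinal or both, for the likelihood of a good outcome (mRS 2 or less in section V.A). On the covariates it says: "These parameters will include CIS, mTICI score, NIHSS score, time to revascularization, age, sex, history of diabetes mellitus, history of high blood pressure". The ninth is prior coronary disease.

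For the second phase: "The same analyses will be performed for phase II", with treatment group taking the place of CIS.

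On size, section III.A says: "The sample size will be set to have 60 patients complete the trial". Phase II randomizes 30 patients 1:1. Section V.A sizes Phase I on outcome proportions only.

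The plan does not say:
- whether the nine parameters enter one model or several;
- how mTICI and CIS are coded;
- which ordinal outcome would be used;
- what happens if a fit fails.

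It names no variable-selection rule and no penalized or exact method.

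**The concern.** CIS groups are observed, not randomized, and the Fisher tests are unadjusted. This regression is therefore the only planned analysis that separates CIS from age, baseline NIHSS, time and the other listed factors.

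Maximum-likelihood logistic regression with very few events per parameter gives odds ratios biased away from 1. When the covariates can separate the outcomes, it gives no finite estimate at all. An inflated adjusted odds ratio would lend extra support to CIS as a selection tool, which is the trial's stated aim. In Phase II, a failed fit with no stated fallback leaves the model to be chosen after the data are seen.

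**Working it through.** **Inputs.** From sections III.A and V.A:
- Phase I: 60 completers, 60% fCIS, 50% good revascularization. Good-outcome rates are 70% (fCIS, good revascularization), 20% (fCIS, poor), 20% (pCIS, good) and 10% (pCIS, poor).
- Phase II: 15 per arm. About 13% good outcomes are expected with IAT. There are no prior data for the other arm, which is put at 25% at best.

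**The plan's own figure.** Treat CIS and revascularization as independent. The fCIS, good-revascularization cell is then 0.6 × 0.5 = 30% of patients. The rate in all others is (0.30 × 0.2 + 0.20 × 0.2 + 0.20 × 0.1)/0.70 = 0.12/0.70 = 0.171. Comparing 0.70 with 0.171 at two-sided alpha 0.025, power 0.90, allocation 3:7 and continuity correction needs 16 in the smaller group. That gives 16/0.30 = 53.3, so 54, as stated. The figure reproduces, but it concerns a comparison of proportions and says nothing about a nine-parameter model.

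**Events per parameter.**
- Phase I: 18 × 0.7 + 18 × 0.2 + 12 × 0.2 + 12 × 0.1 = 12.6 + 3.6 + 2.4 + 1.2 = 19.8; 19.8/9 = 2.2.
- Phase II, lower: 15 × 0.13 + 15 × 0.13 = 3.9; 3.9/9 = 0.43.
- Phase II, upper: 15 × 0.13 + 15 × 0.25 = 5.7; 5.7/9 = 0.63.

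Entering the five-level mTICI or the four-level CIS by category would lower these further.

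**Phase I target value.** The plan's rates imply a CIS odds ratio of (0.7/0.3)/(0.2/0.8) = 9.3 with good revascularization and (0.2/0.8)/(0.1/0.9) = 2.25 with poor. A model without interaction settles between them. Its large-sample value in simulation is 5.9.

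**Phase I simulation, n = 60.** The outcome follows the four cell rates. mTICI is two-level and the remaining covariates are unrelated to outcome. Results for 2,000 trials:

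| Fit | CIS odds ratio (large-sample about 5.9) |
|---|---|
| Nine terms, maximum likelihood, finite fits | median 8.3, geometric mean 10.4 |
| CIS and mTICI only, maximum likelihood | median 6.3, geometric mean 6.8 |
| Nine terms, Firth | median 5.3, geometric mean 5.95 |

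- The nine-term log odds ratio is biased upward by about 32%: ln 10.4 / ln 5.9 = 2.34/1.77 = 1.32. About 4% of trials had no finite fit.
- Other runs on the same cell rates put the nine-term median at 8.9 and 9.0. In one, Firth gave geometric means of 6.2 (nine terms) and 6.0 (four terms).
- Type I error at nominal 5% was 7.3–9.3% for the likelihood-ratio test and 5.6–6.3% for the Wald test. Coverage of nominal 95% intervals stayed near 95%, because the intervals are very wide (SD of the log odds ratio about 1.5).

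**Phase II simulation, n = 30, binary model.** A linear program checked each data set for separation. Assumed prevalences: sex 50%, diabetes and coronary disease 20–50%, hypertension 50–80%. Trials with no finite solution:

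| Terms | Control rate 13% | Control rate 25% |
|---|---|---|
| Nine | 72–89% | 52–75% |
| Seven (no mTICI, no time to revascularization) | 59–85% | 37–73% |

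The seven-term row matters because the two dropped covariates are undefined for patients without IAT.

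**Phase II, ordinal model.** Nine terms on the full mRS, with patients spread evenly within mRS 0–2 and within 3–6 (an assumption), had no finite solution in about 0.1% of trials. If the nine-term model has a finite solution, so does any model using a subset of its terms.

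**The case against.** The best defence is that the plan already allows an ordinal model, which on the full mRS almost always has a solution. It also says only that the parameters will include these nine, not that all enter one model. The regression is supportive: no sample-size, stopping or Phase II launch rule uses it. Sections III.A, V.A and VII openly call Phase II small and underpowered, and section V.A calls it exploratory. The covariate prevalences behind the simulations are not in the documents.

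Much of this stands, and it rules out several stronger readings that a reader might infer:
- *Phase II can yield no usable estimate.* Not supported, because the ordinal option is in the plan.
- *The Phase II binary model usually fails.* True of nine terms in every scenario run, but not of seven: the lowest figure is 37%.
- *The significance of CIS is seriously overstated.* The plan names no test. Inflation is mild with the likelihood-ratio test and slight with Wald.
- *The main result is undermined.* The Fisher tests do not depend on this model.

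What does not stand is the idea that the plan has dealt with the problem. It commits to neither model, and its stated target is the binary good outcome. Admitting low power is also different from providing for an estimate that may not exist.

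**Conclusion.** The point holds for the binary model fitted by ordinary maximum likelihood, which the plan permits and its wording suggests. The event counts rest only on the plan's own figures. The upward bias in the Phase I odds ratio, roughly 40–50% at the median (8.3/5.9 = 1.41; 9.0/5.9 = 1.53), was consistent across simulations. The Phase II failure rate is substantial in every scenario, but its size depends on assumed prevalences and on which terms are kept. This is a defect in a supportive analysis, worth correcting before the data are analysed. It does not affect the trial's primary conclusion.

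**What to change.** Change the wording of section V.B.

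- **Phase I:** fit the binary model by Firth-penalized logistic regression with profile-likelihood intervals. The penalty alone removes nearly all the average bias, even with nine terms. A short prespecified list (CIS, revascularization, age, baseline NIHSS) is preferable, since about 20 events cannot support more.
- **Phase II:** prespecify proportional odds on the full mRS with treatment, age and baseline NIHSS. Omit mTICI and time to revascularization, and do not fit the binary multivariable model.
- **Both phases:** report sex, diabetes, hypertension and coronary disease descriptively by group.

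The cost is SAP text, with no new data or patients. Adjusted estimates for those four factors are given up, and Phase II takes on the proportional-odds assumption, which 30 patients can barely test. The change makes the Phase II model estimable; it does not make Phase II adequately powered.

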In phase II, after confirming the hypothesis that patients with pCIS tend to have poor outcomes as compared to the natural history of the disease, only patients with pCIS will be enrolled. 30 patients will be randomized into treatment including IAT or without IAT plus standard of care based on a simple 1:1 randomization. All otherwise IV tPA eligible patients will be treated with IVT using tPA regardless of the assigned group since this represents current standard of care. Based on previous studies, the results from Phase I should show poor results for pCIS patients, on the order of 15% good outcomes, below the published good outcomes for patients receiving no treatment. This phase will provide preliminary data to determine if IAT provides any benefit in these patients, or is even potentially harmful, which no other clinical trial to date of IAT has formally hypothesized or tested as plausible. Due to the low rate of success the investigators realize this phase will be underpowered to definitively show differences between two groups, but the phase will provide preliminary safety pilot data on a topic not studied to date to develop plans for a larger and adequately powered study.

All eligible patients participating in both phase I and phase II will be given the option to donate an additional 8.5 ml blood sample for genetic testing of the *Dce1* gene. Blood samples will be collected in Paxgene DNA tubes. Collection of this sample will occur during regularly scheduled blood work within 48-60 hours of admission. Akron General will store all samples until all patients are enrolled after which the samples will be sent to a biospecimen processing facility to identify polymorphisms of the *Dce1* gene. Results obtained from the genetic testing will be analyzed in conjunction with data from phase I and II.

The primary measure of outcome will be the same for both phases. The outcomes will be measured based on the modified Rankin Scale (see appendix) at least 3 months and again at 1 year following treatment. Patients will be graded according to this scale by an experienced

Version: 6.0

neurologist or other mRS scale certified health care provider not involved in the treatment and blinded to the treatment for each patient.

B. Study Population:

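### The Phase II regression keeps mTICI and time to revascularization, which the no-IAT arm lacks, so its treatment coefficient is either not estimable or not the total effect of assignment to IAT.

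*Combined protocol and SAP*

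**What the plan says.** Section V.B (Statistical Methodology) plans Fisher exact tests and binary and/or ordinal multiple logistic regression. On the regression it states: "These parameters will include CIS, mTICI score, NIHSS score, time to revascularization, age, sex, history of diabetes mellitus", followed by histories of high blood pressure and coronary artery disease. Phase II gets one sentence: "The same analyses will be performed for phase II, instead focusing on the treatment groups rather than the CIS classification". No covariate other than CIS is removed, and no separate Phase II model appears elsewhere.

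Section III.A gives the Phase II design: "30 patients will be randomized into treatment including IAT or without IAT plus standard of care based on a simple 1:1 randomization". In Phase I, by contrast, every patient receives IAT.

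Section III.D fixes when mTICI is graded: "Adequacy of revascularization will be assessed at the end of treatment by the treating physician". Section IV.A lists the times collected as symptoms to arrival, "time to start of DCA, and time to end of the procedure". Neither section provides an end-of-treatment mTICI, a revascularization time or a missing-data rule for patients who have no IAT.

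**The concern.** In Phase I the two variables exist in principle for everyone. In Phase II they are products of one of the two randomized treatments. A statistician following V.B literally has to do something with the control arm, and the obvious choices all fail:

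- **Leave the values missing.** A complete-case fit loses every control.
- **Code controls as not revascularized.** The model then conditions on a consequence of treatment.
- **Measure recanalization in controls.** The model then removes the part of the IAT effect that works through opening the vessel.

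Section III.A wants Phase II to give preliminary data on whether IAT helps or harms pCIS patients, as a basis for a larger trial. An adjusted odds ratio that is missing, or that answers another question, is poor input for that. With no rule in the plan, the coding of controls could also be chosen after the data are seen.

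**Working it through.** **Inputs from the protocol**

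- 30 patients, 1:1, so about 15 per arm (III.A).
- Share revascularized r = 0.50 (V.A, Phase I). Recanalization rates of up to 80–90% are cited in I.C, so 0.90 is also tried.
- Good outcome (mRS 2 or less) in pCIS: 20% with good and 10% with poor revascularization (V.A, Phase I).
- For Phase II, V.A says: "The rate of good outcomes is expected to be approximately 13% for the IAT group with revascularization".
- Untreated rates: about 20% (I.D) and about 25% as the best case (V.A, Phase II).

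**Assumptions, not in the protocol**

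- No-IAT good-outcome rate pc: 10% to 25%.
- Rate without revascularization: 13% under futility, and 20% or 25% under harm (set equal to the two untreated rates).

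**The plan's own figure.** 0.5 × 20% + 0.5 × 10% = 15%. This agrees with the rate of about 15% that III.A expects for treated pCIS patients. No Phase II sample size calculation exists to reproduce.

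**Controls missing.** Only the 15 IAT patients remain and treatment is constant. The design matrix with intercept, treatment, mTICI and time has 4 columns and rank 3, so the treatment coefficient is not estimable.

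**Controls coded as not revascularized (binary).** Let g and p be the good-outcome rates in IAT patients with and without revascularization. The three occupied cells saturate the model, so:

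- IAT-arm rate t = r·g + (1 − r)·p
- total-effect OR = odds(t)/odds(pc)
- adjusted OR = odds(p)/odds(pc)
- distortion factor = odds(p)/odds(t), whatever pc is

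| g / p | t at r = 0.5 | odds(p)/odds(t) | factor, r = 0.5 | factor, r = 0.9 |
|---|---|---|---|---|
| 20% / 10% | 15.0% | 0.1111/0.1765 | 0.63 | 0.47 |
| 13% / 13% | 13.0% | 0.1494/0.1494 | 1.00 | 1.00 |
| 13% / 20% | 16.5% | 0.2500/0.1976 | 1.27 | 1.57 |
| 13% / 25% | 19.0% | 0.3333/0.2346 | 1.42 | 2.01 |

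At 20%/10% and r = 0.5, by assumed control rate:

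| pc | total-effect OR | adjusted OR |
|---|---|---|
| 10% | 1.59 | 1.00 |
| 13% | 1.18 | 0.74 |
| 15% | 1.00 | 0.63 |
| 20% | 0.71 | 0.44 |
| 25% | 0.53 | 0.33 |

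In the harm rows at r = 0.5, with controls also at 20% or 25%, a true OR of 0.1976/0.2500 = 0.79 or 0.2346/0.3333 = 0.70 becomes 1.00.

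**Graded mTICI.** Scored 0–4 and entered linearly, controls at 0, pc = 20%. Three IAT distributions were assumed, each with 50% at 2b/3: 10/10/30/30/20, 20/10/20/25/25 and 5/5/40/40/10. The factors are 0.38–0.54, 1.00, 1.38–1.68 and 1.62–2.19 for the four rows of the first table. The directions are unchanged. Time to revascularization has no natural control value and was not modelled.

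**Control recanalization measured.** Take an assumed share q of 5% to 30% and the same 20%/10% rates. The control rate is q·20% + (1 − q)·10%, that is 10.5% to 13%. The total-effect OR is 1.50 to 1.18, but the adjusted OR is 1.00 throughout.

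**Sparse cells at 20%/10%, r = 0.5**

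- No good outcome among poorly revascularized IAT patients: (1 − 0.5 × 0.10)^15 = 0.46.
- Non-finite OR, unadjusted: 1 − (1 − (1 − pc)^15)(1 − 0.85^15) = 0.28 at pc 10%, 0.10 at pc 25%.
- Non-finite OR, revascularization in the model: replace 0.85 by 0.95, giving 0.57 and 0.47.
- SE of the treatment log OR at pc = 15%: √(2/(15 × 0.15 × 0.85)) = 1.02 unadjusted, and √(1/(15 × 0.15 × 0.85) + 1/(7.5 × 0.10 × 0.90)) = 1.42 with revascularization.
- Expected good outcomes in Phase II: 15 × 0.15 + 15 × (0.10 to 0.25) = 3.75 to 6.0, for nine model terms (treatment plus eight covariates).

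**The case against.** V.B describes the regression as looking at several influences on outcome, and nowhere names its treatment coefficient as the Phase II effect estimate. The same-analyses sentence also carries over the Fisher test, which leads in Phase I, so the unadjusted comparison arguably already leads in Phase II. The protocol repeatedly calls Phase II underpowered and preliminary. The sentence is a summary, and that both variables stay in the model is inferred from it. The ways of handling controls are constructions, since the protocol specifies none.

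On size, the investigators' own expectation in I.D is futility, for which the factor is 1.00. The factors above 1 assume that poorly revascularized IAT patients do as well as untreated patients (20–25%), while the only protocol figure for that cell is 10%. The 20%/10% pair is a Phase I planning assumption, and I.D and VIII.B raise harm as a question and a risk, not as a finding. Against a standard error of at least 1.02, factors such as 0.63 or 1.27 are small.

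Most of this stands as a limit on the consequence. None of it supplies a control-arm value or a coding rule. Phase II patients need a DCA for CIS, so a pre-treatment grade could exist in controls, but that is not the end-of-treatment mTICI defined in III.D. Conditioning on a post-randomization variable remains an error whichever value is used.

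**Conclusion.** The concern holds and should be fixed. Read as written, V.B gives a Phase II treatment coefficient that is not estimable or is not the total effect of assignment to IAT. The direction of error is not fixed, because it depends on what revascularization does in pCIS. At 50% revascularized the adjusted OR understates IAT by a factor of 0.63 under the V.A rates, is undistorted under futility, and is inflated by 1.27 to 1.42 under harm. The last case could conceal the harm the investigators suspect, but it rests on assumed rates of 20% or 25% without revascularization. The control rate is assumed throughout, though the binary-model factors do not depend on it. The impact is limited to the adjusted estimate: the unadjusted comparison of randomized arms needs neither variable and remains valid.

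**What to change.** State three things for Phase II in V.B:

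1. The treatment model contains randomized treatment and baseline covariates only (emergency-room NIHSS, age, sex, diabetes, hypertension, coronary artery disease). It excludes mTICI and time to revascularization.
2. The unadjusted randomized comparison of good-outcome rates is the main Phase II result.
3. mTICI, procedure times and the Fisher test on revascularization are reported within the IAT arm only.

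Phase I is unchanged.

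A separate step is advisable. With about 4 to 6 good outcomes expected, six baseline covariates are still too many. A simulation under assumed covariate distributions showed separation in about 53–80% of trials, a figure that is only indicative. Fewer covariates or a penalized fit should be specified.

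The cost is wording only, with no new data, visits or patients. The loss is that Phase II gives no model-based revascularization effect across both arms, only a description in about 15 IAT patients. The unadjusted estimate stays imprecise: 2/15 against 4/15, for example, is a difference of −13 percentage points with a Newcombe 95% CI of about −40 to +16.
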